5.6 Growth

5.6.1 Standing height/recumbent length Z-score and Percentile

Recumbent length will be measured in subjects < 2 years old or those unable or unwilling to stand for the measurement. Standing height/recumbent length measurements prior to treatment will be abstracted from medical records where available.

Growth as measured by standing height or recumbent length will be evaluated on a percentile basis using the Centers for Disease Control/National Center for Health Statistics (CDC/NCHS) Clinical Growth Charts ([Kuczmarski et al. 2000](#)). Data used to produce the United States Growth Charts smoothed percentile curves will be downloaded from the official CDC/NCHS web site: http://www.cdc.gov/growthcharts/percentile_data_files.htm

The data files from the CDC/NCHS that are used for this analysis are summarized below. These files represent the different growth curves for children. LMS refers to the parameters in the CDC Growth Charts Percentile Data Files used to construct the growth curves; these are: the power in the Box-Cox transformation (L); the median (M); and the generalized coefficient of variation (S).

The data files used are:

- Length-for-age charts, birth to 36 months, LMS parameters and selected smoothed recumbent length percentiles in centimeters, by sex and age (LENAGEINF).
- Stature-for-age charts, 2 to 20 years, LMS parameters and selected smoothed stature percentiles in centimeters, by gender and age (STATAGE).

Calculation of Z-scores for length/stature values above and below the median will be performed. Using the CDC/NCHS Clinical Growth Charts, the height-for-age Z score will be calculated using the following equation:

$$Z = \{(X/M)^L - 1\} / (L \times S),$$

where X is the physical measurement (stature in cm) and the LMS parameters are obtained from the appropriate CDC/NCHS Clinical Growth Chart corresponding to the age in months of the child. The percentile corresponding to the Z score is then the corresponding percentile from the standard normal distribution.

5.6.2 Weight Z-score and Percentile

Weight will be evaluated by z score and percentile using the same method as Section 5.7.1 based on Centers for Disease Control/National Center for Health Statistics (CDC/NCHS) Clinical Growth Charts ([Kuczmarski et al. 2000](#)). The data files used for weight Z-score and percentile are:

- Weight-for-age charts, birth to 36 months, LMS parameters and selected smoothed weight percentiles in kilograms, by sex and age (WTAGEINF).
- Weight-for-age charts, 2 to 20 years, LMS parameters and selected smoothed weight percentiles in kilograms, by sex and age (WTAGE).

5.7 Blood Pressure Percentile

The blood pressure percentile will be derived based on the Fourth Report on the Diagnosis, Evaluation and Treatment of High Blood Pressure in Children and Adolescents ([NHLBI 2005](#)). See [Appendix 6](#) for details in deriving blood pressure percentile adjusting for age, gender and height.

5.8 Heart Rate Percentile

The heart rate percentile category will be derived based on the National Health Statistical Reports on resting pulse rate reference data for children, adolescents, and adults: United States, 1999-2008 ([Ostchega et al. 2011](#)). See [Appendix 7](#) for details in deriving heart rate percentile category adjusting for age and gender.

5.9 Events to Monitor

The definition for each type of adverse events to monitor is as follows:

- Injection Site Reaction is defined by preferred terms under the Medical Dictionary for Regulatory Activities (MedDRA) high-level term (HLT) “Injection site reaction”.
- Immunogenicity AE: Defined using relevant PTs in the narrow SMQs for “Hypersensitivity”.
- Hyperphosphatemia AE: Defined by using PTs: “Hyperphosphataemia”, “Blood phosphorus increased”, “Blood phosphorus abnormal”.
- Ectopic calcification related AE: There is no available SMQ. Ectopic calcification related AE is defined using a MedDRA search of ‘calcification’.
- Restless leg syndrome AE: Defined by PTs “Restless legs syndrome”, “Restlessness”, “Akathisia”, “Sensory disturbance”, “Psychomotor hyperactivity”, “Limb discomfort”, “Neuromuscular pain”, “Formication”.

Please see the search criteria in [Appendix 8](#) for more details.

5.10 Dose Limiting Toxicity

A DLT is defined as the occurrence of any of the following:

- Unexpected SAEs occurring during treatment considered to be either definitely, probably, or possibly related to the investigational product
- A confirmed serum phosphorus level of ≥ 6.5 mg/dL (defined as hyperphosphatemia) at any time after dosing

If a subject experiences a DLT, the planned dosing for that subject will be evaluated by the Investigator and medical monitor. The outcome of this investigation will determine the subjects' continuation or withdrawal from the study.

5.11 Duration of SOC

The definition for duration of SOC is as the following:

Duration of SOC = End date of the last SOC taken - start date of first SOC taken + 1 day

If the date is partially or completely missing, apply the following imputation rule:

Start Dates

- If the FIRST start date of SOC is completely missing, then use the next earliest non-missing date.
- If the year is known and month is missing, then assign 'January 1st';
- If the year and month are both known and day is missing, then assign the first day of the month.

Stop Dates

- If LAST stop date is completely missing, then impute 'one day' prior to the informed consent date
- If year is known the month is missing, then assign "December 31st". If this imputed date is after the informed consent date, use one day prior to the informed consent date instead.

If year and month are both known and the day is missing, then assign the last day of the month. If this imputed date is after the informed consent date, use one day prior to the informed consent date instead

6 ANALYSIS POPULATIONS

6.1 Efficacy Analysis Set

The Efficacy Analysis population will consist of all subjects who receive at least one dose of study drug and have at least one post-study drug measurement of serum phosphorus.

6.2 Safety Analysis Set

The Safety Analysis Set will consist of all subjects who receive at least one dose of study drug.

6.3 Pharmacokinetic (PK) and Pharmacodynamic (PD) Analysis Set

The PK/PD analyses sets will consist of all subjects who receive at least one dose of study drug and have evaluable blood samples.

7 DATA SCREENING AND ACCEPTANCE

7.1 General Principles

Data will be reviewed periodically. Any questionable data will be reported to clinical data manager promptly for query and resolution.

7.2 Handling of Missing and Incomplete Data

Missing clinical outcome data can occur for multiple reasons, including missed subject visits and scales or measures with missing item scores. Missing and incomplete data will be identified through a review of tables and listings for this study. Missing and incomplete data will be identified for investigation, and possible resolution, by Data Management prior to the study database lock or database snapshot.

If not specified, only the actual data (not imputed data) will be presented in listings.

7.2.1 Missing Date Information for Adverse Events and Concomitant Medications

The following conventions will be used to impute missing portions of dates for adverse events and concomitant medications. Note that the imputed values outlined here may not always provide the most conservative date.

Missing Start Dates

- If the day is unknown, then:
 - If the month and year match the first dose of investigational product start date month and year in this study, then impute the day of the first dose date.
 - Otherwise, assign the first day of the month.
- If the month is unknown, then:
 - If the year matches the year of the first dose of investigational product date in this study, then impute the month and day of the first dose date in this study.
 - Otherwise, assign ‘January’
- If the year is unknown, then the date will not be imputed and will be assigned a missing value.
- If the imputed date is earlier than birth date, then birth date will be used.

Missing Stop Dates for events not ongoing

- If the day is unknown, then assign the last day of the month.
- If the month is unknown, then assign ‘December.’
- If the year is unknown, then the date will not be imputed and will be assigned a missing value, and the event will be considered ongoing. If the AE has been recorded

as resolved/recovered, all efforts should be made to obtain the date from the Investigator.

- If the resulting end date is after the date of study completion / discontinuation/ data cutoff, set the imputed end date as the date of study completion / discontinuation/ data cutoff.

If the year is missing for the start date, and stop date (observed or imputed) is on or after the first dose or event is ongoing. The start date will be imputed as the first dose date.

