8.6 Prior and Concomitant Medication

Prior medication is defined as any medication started before the date of the first dose of investigational product (medication start date prior to the first dose date). Concomitant medication is defined as any medication taken on or after the date of the first dose of investigational product [medication end date on or after first dose date (or ongoing), and medication start date prior or on the last dose date]. Any concomitant medications started after the date of the last dose of investigational product will not be presented in the summary tables but will be included in the subject data listings. If start date is completely missing and end date is before first dose date, the medication will be considered as prior, otherwise it will be considered as concomitant.

Both prior and concomitant medications will be coded by drug name and therapeutic class using WHODRUG version 2015Q3 or the latest version at the time of snapshot/database lock. If a subject took a specific medication multiple times or took multiple medications within a specific therapeutic class, that subject would be counted only once for the coded drug name or therapeutic class.

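### SAP 5.11 can date the start of standard of care before the child's birth; and, if 7.2.1 is applied to all medications, a drug stopped before dosing can be neither prior nor concomitant

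*SAP*

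**What the plan says.** **SOC duration.** SAP 5.11 defines it as last stop minus first start plus one day and gives its own rules for partial dates. A start with only the year known becomes 1 January; a start lacking only the day becomes the first of the month. The only limit in 5.11 is on imputed stop dates, which may not run past consent. Section 8.5 lists SOC duration and age at SOC initiation as baseline characteristics.

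**Adverse events and medications.** SAP 7.2.1 sets out to "impute missing portions of dates for adverse events and concomitant medications". It has a birth-date floor: "If the imputed date is earlier than birth date, then birth date will be used". Two branches move a partial start to the first-dose date. With the day unknown: "If the month and year match the first dose of investigational product start date month and year in this study, then impute the day" of first dose. With the month unknown: "If the year matches the year of the first dose of investigational product date in this study, then impute the month and day" of first dose. Neither looks at the stop date. Only the missing-year rule does: "If the year is missing for the start date, and stop date (observed or imputed) is on or after the first dose" (or the event is ongoing).

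**Classification.** SAP 8.6 says "Prior medication is defined as any medication started before the date of the first dose of investigational product". A concomitant medication needs "medication end date on or after first dose date (or ongoing), and medication start date prior or on the last dose date". The section's fallback covers only a completely missing start.

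**The concern.** The trial enrols children aged 1 to 4, some already treated, so an SOC start in the year of birth is plausible. Rounding a year-only date back to 1 January then places the start before the child existed. SOC duration can exceed the child's life, and age at SOC initiation can be negative if it uses the same date, which the SAP does not say. With about 10 subjects, one such record is visible in a mean and sets the extreme of the range.

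The two first-dose branches of 7.2.1 raise a separate difficulty if they are run on every collected medication. A drug started and stopped before dosing, within the first-dose year or month, gets a start later than its own stop. Neither definition in 8.6 then captures it, and the prior-medication table can omit a drug the child took.

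**Working it through.** The plan states no figure to reproduce. The rules were applied as written; **all calendar dates below are assumed**.

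**1. SOC duration (5.11).** Birth 1 Sep 2013; SOC start recorded only as 2013; consent 5 Apr 2016; SOC taken to the day before consent.

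- Imputed start: 1 Jan 2013, which is 243 days before birth.
- Duration as written: (4 Apr 2016 − 1 Jan 2013) + 1 = 1,190 days.
- Age at consent by the 5.3 day count: (5 Apr 2016 − 1 Sep 2013) + 1 = 948 days.
- Duration with a birth-date floor: (4 Apr 2016 − 1 Sep 2013) + 1 = 947 days. Difference: 1,190 − 947 = 243 days.
- Age at SOC initiation, if it used the same date and the 5.3 count: (−243 + 1)/365.25 = −0.66 years.

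The true start lies between 1 Sep and 31 Dec 2013, a span of 121 days. The true duration is therefore between 947 − 121 = 826 and 947 days. The rule as written overstates it by 243 to 364 days; with the floor, the overstatement is 0 to 121 days.

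**2. How far before birth.** For a year-only start in the birth year, the offset is the birth date minus 1 January: 31 days for 1 Feb, 181 for 1 Jul and 364 for 31 Dec (the last two are one day more in a leap year). Only a birth on 1 January gives zero. With only the day missing and the start in the birth month, the offset is at most 30 days.

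**3. Effect on a mean.** Relative to the floored value, one record moves the mean by offset/n, where n is the number of children in the SOC summary. For the example, 243/10 = 24.3 days if all of about 10 children had SOC, and 243/5 = 48.6 days if half did. Treatment-naïve children are eligible, so n may be below 10.

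**4. Medications (7.2.1 then 8.6), if 7.2.1 is applied to all collected medications.** First dose 17 May 2016.

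| Recorded start | Stop | Imputed start | Stop − start | Prior? | Concomitant? |
|---|---|---|---|---|---|
| 2016 | 10 Mar 2016 | 17 May 2016 | −68 days | No | No |
| May 2016 | 9 May 2016 | 17 May 2016 | −8 days | No | No |
| 2015 | 10 Mar 2016 | 1 Jan 2015 | positive | Yes | No |
| Completely missing | 10 Mar 2016 | none | – | Yes (8.6 fallback) | No |

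The first two rows fail: the start is not before first dose, and the end is. Using the first day of the known period (1 Jan or 1 May 2016) makes both prior.

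**5. Exposed window.** The drug must start and stop between 1 January (or the first of the month) and the day before first dose. For 17 May 2016 that is 137 days for a year-only start and 16 days for a day-unknown start. In general, the day-unknown window is the day of the month minus one, so 0 to 30 days. The stop must be observed, or imputed to a month-end before dosing. A stop with its month unknown in the first-dose year goes to December or the end-of-study cap, so that record counts as concomitant.

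**The case against.** **Scope of 7.2.1.** Its heading and opening sentence name only adverse events and concomitant medications. Read literally, a drug with an observed stop before dosing is not concomitant, so its start is never imputed and it is plainly prior. This stands as far as making the medication point conditional. Against it, 8.6 decides concomitant status from the dates and has no other rule for partial starts, and the schedule collects these records from Screening. Imputing before classifying is therefore the more workable reading.

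**Does the broad reading bring the 7.2.1 floor to SOC?** It could be argued. But 5.11 has its own imputation rules for SOC duration and does not refer to 7.2.1, so the specific section governs.

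**Would review catch it?** A reader might infer that these errors go unseen. The documents do not support that for SOC: 8.1 puts derived data in listings and reports the minimum and maximum, so an impossible duration or negative age could be noticed. Data queries may also complete some dates. The medication conflict is harder to see, because the raw record is consistent and, unless specified otherwise, "only the actual data (not imputed data) will be presented in listings".

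**Adverse events.** A reader might also infer that events resolved before dosing become treatment-emergent. Such an event could carry an impossible start date, but 8.10.1 excludes events already present before first dose unless they worsen.

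**The SAP's caveat.** 7.2.1 warns that imputed dates may not be the most conservative. That does not cover a start after its own stop, and it does not apply to 5.11.

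**Conclusion.** The 5.11 point holds as written: a year-only SOC start in the birth year precedes birth unless the child was born on 1 January, and the resulting duration can be impossible. The medication point holds only if 7.2.1 is run on all collected medications before 8.6 classifies them.

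Both are minor. They touch the baseline SOC summaries and the prior-medication tables. The latter change only if the child has no other dated record of that drug or class. The SAP gives no means of counting affected records. No efficacy endpoint is affected, SOC duration is not a named covariate, and treatment-emergent status under 8.10.1 is unaffected.

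The 243-day gap in the example is measured against a start at birth, not against the true start. It shows the impossible part of the duration, and a floor removes that part only.

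**What to change.** **In 5.11, add:** *If the imputed SOC start date is before birth, use the birth date; use the same date for age when SOC initiated.*

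**In both first-dose branches of 7.2.1, add:** *Use the first-dose date only if the stop date (observed or imputed) is missing, ongoing, or on or after first dose; otherwise use the first day of the known month or year, not before birth.*

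**Also in 7.2.1,** state that the section covers prior as well as concomitant medications.

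The cost is three sentences in the SAP and a few lines of derivation code. Both safeguards already exist elsewhere in 7.2.1.

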7.2.2 Missing Causal Relationship to Investigational Product for Adverse Events

If the causal relationship to the investigational product is missing for an AE that started on or after the date of the first dose of investigational product, a causality of “definitely related” will be assigned. The imputed values for causal relationship to investigational product will be used for the incidence summary; the values will be shown as missing in the data listings.

7.3 Unscheduled and Early Termination Visits

Unscheduled visit occurred prior to or on the date of initiation of the first dose will be mapped to the baseline visit if it is the last assessment prior to or on the date of initiation of the first dose; otherwise no mapping will be performed.

Unscheduled visits that occurred after the date of initiation of the first dose will be mapped to the post-baseline scheduled visit with the closest target study day (refer to Section [5.2](#) for study day definition and [Appendix 3](#) for the schedule of events). If the unscheduled visit is in the middle of two scheduled visits, map to the later scheduled visit.

For descriptive summary tables, when more than one measurement is mapped to the same scheduled visit, the measurement taken on the scheduled visit will be used if it is not missing, otherwise the one closest to the target day will be used. If two or more visits have equal distances to the target day, then the later one will be used. If more than one measurement is collected on the same day, use the time or the sequence number to select the latest record.

For listings and shift tables, all data points will be included.

Early termination visit will generally follow the same rule as unscheduled visit except for a special case in X-rays. X-rays will not be performed at the early termination visit if the assessment was conducted within 3 months of termination. Hence if a subject has X-rays at both Week 40 and early termination visits, the X-rays on early termination visit will be mapped to Week 64.

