3.5 Sample Size Considerations

The study will enroll approximately 10 pediatric subjects between 1 and 4 years old, inclusive, with clinical findings consistent with XLH including hypophosphatemia and radiographic evidence of rickets (at least 5 subjects will have a rickets severity score (RSS) at the knee of ≥ 1.5 points at Screening), and a confirmed *PHEX* mutation or variant of uncertain significance. To maintain a level of gender balance, no more than 7 subjects of either gender will be enrolled.

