8.10.2 Safety Lab Parameters

Clinical laboratory data will be summarized by the type of laboratory test. Descriptive statistics will be calculated for each laboratory analyte at baseline and at each scheduled time point. Shift table for iPTH at each scheduled visit will be provided to assess to the normality over time. The frequency and percentage of subjects who experience abnormal clinical laboratory results and/or clinically significant abnormalities will be presented for each clinical laboratory measurement.

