8.10.5 Renal Ultrasound

Renal ultrasound will be conducted with findings of nephrocalcinosis graded on a 5-point scale by a central reader. The renal ultrasound is read using a pre-defined methodology ([Biomedical Systems Independent Review Manual November 2014](#)). These results will be summarized by time point, a grade shift table summarizing changes from Baseline by time point will also be created.

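### By-visit shift tables take every mapped record, so a child with two values at one visit is counted twice and the table has no fixed denominator

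*SAP*

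**What the plan says.** Section 7.3 of the SAP handles values outside the schedule in three steps.

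- **Mapping.** A post-dose unscheduled visit "will be mapped to the post-baseline scheduled visit with the closest target study day". Early termination visits generally follow the same rule, with a special case only for X-rays.
- **Selection for descriptive tables.** Here "when more than one measurement is mapped to the same scheduled visit, the measurement taken on the scheduled visit will be used", provided that a value exists. Failing that, the value nearest the target day is taken, with tie-breaks.
- **Selection for listings and shift tables.** There is none: "For listings and shift tables, all data points will be included".

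The SAP specifies two shift tables, both by visit. Section 8.10.2 says "Shift table for iPTH at each scheduled visit will be provided to assess to the normality over time". Section 8.10.5 says that for renal ultrasound "a grade shift table summarizing changes from Baseline by time point will also be created". Section 8.1 calls for frequencies and percentages for discrete data. No section gives the counting unit or the denominator for a shift table.

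**The concern.** A by-visit shift table is read as a cross-classification of children: each child has one baseline category and one category at the visit, and the cells add to the number of children seen. The rule in 7.3 breaks this as soon as one child has two values mapped to the same visit. That child then appears twice in one cell or once in each of two cells, and the table becomes a mixture of children and records. For the same visit, the iPTH descriptive table (one value per child) and the iPTH shift table (all values) would report different n.

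This matters mainly because the trial is small. With about 10 children, one extra record moves a percentage by a visible amount, in tables meant to show whether iPTH normalises and whether nephrocalcinosis grade changes.

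**Working it through.** The SAP states no figure on this point, so there is none to reproduce. The check is a direct count.

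**Inputs**

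- n = 10 children. Section 3.5: "The study will enroll approximately 10 pediatric subjects between 1 and 4 years old, inclusive".
- k = children abnormal at the scheduled visit. Assumed 1 to 3.
- r = repeats per abnormal child mapped to that visit. Assumed 1 or 2.
- q = share of those repeats that are abnormal. The extremes 0 and 1 are shown.

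The SAP gives no values for k, r or q.

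**Formulas**

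- One record per child: k / n.
- All records, with records as denominator: (k + k·r·q) / (n + k·r).
- All records, with children as denominator: the cells add to (n + k·r) / n.

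**Results, records as denominator**

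| k | r | One record per child | All records, repeats abnormal (q = 1) | All records, repeats normal (q = 0) |
|---|---|---|---|---|
| 1 | 1 | 1/10 = 10.0% | 2/11 = 18.2% | 1/11 = 9.1% |
| 1 | 2 | 1/10 = 10.0% | 3/12 = 25.0% | 1/12 = 8.3% |
| 2 | 1 | 2/10 = 20.0% | 4/12 = 33.3% | 2/12 = 16.7% |
| 3 | 1 | 3/10 = 30.0% | 6/13 = 46.2% | 3/13 = 23.1% |

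The all-records share exceeds the per-child share only when q > k/n. Below that it is too low.

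**Results, children as denominator (k = 1, r = 1)**

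- Repeat abnormal: normal 9/10 = 90%, abnormal 2/10 = 20%, total 110%.
- Repeat normal: normal 10/10 = 100%, abnormal 1/10 = 10%, total 110%.

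In every k = 1, r = 1 case the shift table holds 11 entries while the descriptive table for that visit holds 10.

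**How a duplicate can arise without any retest.** After baseline, the schedule of events (Appendix 3) places renal ultrasound only at Week 40 and Week 64/early termination. Suppose the mapping runs over visits at which ultrasound is scheduled, which 7.3 does not spell out. The midpoint is (40 + 64)/2 = Week 52. An early termination ultrasound before Week 52 then maps to Week 40, where the child may already have a reading.

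**The case against.** The separation in 7.3 looks deliberate: descriptive tables are kept clean, while shift tables keep unscheduled safety values from disappearing. That aim is sound. Under a one-record rule alone, a child who is normal at the scheduled visit and abnormal on an unscheduled test would drop out of the abnormal cell, so a fix has to preserve such values.

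The stakes are also limited. Section 8.10.2 separately plans the number and percentage of subjects with abnormal results for each laboratory measurement, and 8.10.5 summarises ultrasound results by time point apart from the shift table. Ectopic mineralization also has an event-to-monitor category and ECG data. No test or confidence interval is attached to a shift table, and with about 10 children and complete listings any duplicate can be traced.

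A reader might infer more: that repeats follow abnormal results, so the shift tables overstate abnormality. The SAP does not support this. The only result-driven repeats it describes are for serum phosphorus (Section 3.2), and no phosphorus shift table is specified. For iPTH and ultrasound, the SAP ties neither repeats nor the timing of early termination to the result. Nor is 110% a general result. It requires children as the denominator, and the SAP does not fix one.

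None of this removes the double count, which needs only one child with a second mapped value. Table record selection is the SAP's own subject, and no other section corrects the rule.

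**Conclusion.** The point holds as a minor defect in a stated rule. Mapping in 7.3, all records in shift tables, and by-visit shift tables in 8.10.2 and 8.10.5 together allow one child to be counted more than once at a visit, and make the shift table's n differ from the descriptive n.

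The size rests on assumed repeats. With 10 children, one abnormal and one repeat for that child, the record-based abnormal share is 18.2% or 9.1% instead of 10.0%, or else the cells add to 110% over children. The direction is uncertain, so this is a fault of counting and denominator and not a demonstrated bias toward abnormality. If no child has two values mapped to one visit, nothing changes. The primary endpoint and all inferential analyses are untouched.

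**What to change.** Replace the last rule on record selection in 7.3 with wording such as: *Listings show every record. By-visit shift tables use one record per subject per visit, chosen by the rule above, with subjects as the denominator.*

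To keep unscheduled abnormal values visible, add a shift from baseline to the worst post-baseline value per subject, using all records. For nephrocalcinosis, worst is the highest grade. For iPTH, state the direction, or show the highest and lowest values separately.

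The cost is a short change of wording and one extra small table. No abnormal value is lost, since the listings and the worst-value shift retain all of them.
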